- S. Methods for handling missing data use of tabulation and/or other presentation methods It is expected that there will be some missing data. Imputation techniques, such as linear interpolation and multiple imputation methods will be examined to assess the robustness on the results. Completer analyses will also be done based on participants who remained in the study throughout the 6-month follow-up period. When large fractions of information are missing, we will perform sensitivity analyses under weaker assumptions (e.g., non-ignorable missingness). It is recognized, however, that the best approach to missing data is to make all efforts to minimize it, since imputation is difficult when the missing data are non-ignorable or not missing at random. We will attempt to collect outcome data from all participants at all timepoints regardless of whether they continue or complete the study treatment. We will also attempt to collect reasons for missing data when possible. Also, the telephone CAPS assessment can facilitate completeness by enhancing the convenience for participants, who will not have to travel for assessment sessions.

T. Methods for handling outliers

Data edits will identify outliers. Sites will receive data query reports and be asked to modify values or verify current value in database is correct.

U. Identification of fixed or random effects models

Linear mixed effects models (SAS PROC MIXED) will be used to compare the primary outcome between the two treatment groups. The mixed effects model will include time, treatment, treatment by time interaction and site as fixed effects, and participant and therapist as random effects.

V. Methods for handling withdrawals and protocol deviations

Tallies will be reported. Data Monitoring Committee and study's Executive Committee may be asked for recommendations on how to handle these (e.g., should erroneously randomized participant be allowed to continue participation after participant found to be ineligible)

W. Methods for point and interval estimation

See Section II.H above for individual study outcomes. In general, summary statistics will include mean, SD, and range for continuous variables, percentage for categorical variables, and 95% confidence intervals when appropriate.

X. Approach to handling concomitant medications

Reported as percentage of participants who were on a given medication at some time during the study

Y. Planned sample size re-estimation

There is no plan to re-estimate the sample size.

Summary of Updates to Statistical Analysis Plan

Version Number	Version Date	Details of Major Changes
1	02/21/2014	Initial plan
1.1	04/15/2014	From first DMC meeting, 02/25/2014:
		Section II.D: The second DMC meeting will be held one year after recruitment starts, and subsequent meetings will be held at about 6 months interval, either in conference calls or in person.
		Section II.D.1: The DMC requested to see all SAEs as they are reported to the study team.
		Section II.D.2: The DMC agrees with what is written in the protocol that there should be no early stopping for efficacy or futility; however, DMC requested CSPCC to calculate means and standard deviations of outcome data by treatment group in each DMC report and also carry out the treatment comparisons.

APPROVAL SIGNATURE AND DATE

[name], MS

Study Biostatistician

[name]

Director, Palo Alto CSPCC

[name]

Study Co-Chair

[name]

[name]

Study Co-Chair

40

[name] Study Co-Chair

4/15/2014

Date (mm/dd/yyyy)

.

.

1/2014

Date (mm/dd/yyyy)

Date (mm/dd/yyyy)

4123/14

Date (mm/dd/yyyy)

Date (mm/dd/yyyy)

Statistical Analysis Plan for CSP 591 (CERV-PTSD); Version 1.1; April 15, 2014

14

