C. Proposed Data Collection Forms

Copies of the proposed data collection forms can be found in Appendix C.

X. BIOSTATISTICAL CONSIDERATIONS

A. Expected Treatment Effect

This study is a prospective randomized clinical trial aimed to compare the effectiveness of Prolonged Exposure (PE) to Cognitive Processing Therapy (CPT) for the treatment of PTSD in veterans. The primary outcome is the change of CAPS total score from baseline (pretreatment) to the average in the six months post-treatment (measured at immediate posttreatment, 3 and 6 months follow-up visits). We chose to use the average in the six months post-treatment in the definition of primary outcome (versus using a single post-treatment timepoint) because we anticipate that improvement established during the course of treatment will be sustained in the 6 months after treatment for both PE and CPT. Incorporating multiple measurements from the same participant will also reduce the required sample size. The Planning Committee considered an effect size of 0.25 to be a clinically meaningful difference, where the effect size is defined as $\Delta \mu / \eta$, $\Delta \mu$ is the mean difference in the primary outcome between PE and CPT, and η is the standard deviation of the change of CAPS total score from baseline to a specific post-treatment timepoint. By using CSP #494's estimated standard deviation η =19.6, the effect size of 0.25 translates to a $\Delta\mu$ =4.9 points difference in the primary outcome. For simplicity, the sample size for this study is aimed to have 90% power to detect $\Delta \mu$ =5 in the primary outcome.

Cohen (1988) defined 0.25 as a small effect. We have powered the study to detect this difference because both PE and CPT are effective treatments. It is implausible based on existing data to think that the true difference between them is much larger. Conversely, if we did not have adequate power to detect a difference as small as 0.25, then any failure to find a difference between treatments could be seen as inconclusive—which was the problem with the only study that directly compared the treatments ([name] et al., 2002). If the true difference between the effects of PE and CPT is less than 0.25, this would be clinically insignificant.

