Although our sample size calculation is based on DSM-IV CAPS total score data observed in the CSP#494, the effect size of 0.25 is independent of DSM versions. In addition, a correlation coefficient among participants treated by the same therapist is a robust statistics for both location and scale change of CAPS total scores. We expect a negligible difference in inflation factors between DSM versions. Therefore, the sample size derived below is appropriate for CAPS on DSM-5.

B. Sample Size and Power Considerations

1. Planned primary analysis for the primary outcome

Linear mixed effects models (SAS PROC MIXED) will be used to compare the primary outcome between the two treatment groups. The mixed effects model will include time, treatment, treatment by time interaction and site as fixed effects, and participant and therapist as random effects. Specifically let Y_{ijk} denote the CAPS total score measured at timepoint *k* for the *j*th participant treated by therapist *i*. The mixed effects model for the primary analysis is:

$$Y_{ijk} = \alpha + \beta_k + \gamma_{z(i)} + (\beta\gamma)_{kz(i)} + \theta^T w_{ij} + u_i \mathbb{1}_{\{k \neq 0\}} + b_{ij} + \varepsilon_{ijk}$$

where i = 1, ..., I, $j = 1, ..., J_i$, k = 0, 1, 2, 3 with k = 0 indicating baseline and k = 1, 2, 3 indicating the three post-treatment timepoints, z(i) is the treatment that participant j treated by therapist iis randomized to, β_k is the time effect (fixed), $\gamma_{z(i)}$ is the treatment effect (fixed), $(\beta\gamma)_{kz(i)}$ is the time by treatment interaction (fixed), w_{ij} denotes the vector of other covariates in the model (such as site or key baseline characteristics) and θ is the associated regression parameter, u_i is the random therapist effect for therapist i, $1_{\{k \neq 0\}}$ is the indicator for k not equal to zero, b_{ij} is the random participant effect for participant j treated by therapist i, ε_{ijk} is the random error at the k^{th} timepoint for participant j treated by therapist i. While other covariance structures will be used to assess their impact on study results, for simplicity and ease of interpretation we assume in the primary analysis that u_i , b_{ij} and ε_{ijk} are independent and have the following distributions:

$$u_i \sim N(0, \sigma_P^2), b_{ij} \sim N(0, \sigma_{BS}^2), \varepsilon_{ijk}, \sim N(0, \sigma_{WS}^2)$$

Under this mixed effects model, the variance of CAPS total score at timepoint k is

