Because of the large sample size of this study, we expect the randomization process to balance baseline characteristics and produce comparable groups of participants. Baseline comparability between treatment groups will be evaluated with respect to demographic and baseline physical and psychological characteristics. Summary statistics (e.g., means and standard errors for continuous variables, and frequencies and percentages for categorical variables) and graphical techniques (e.g., boxplots for continuous variables, and histograms for categorical variables), will be used to compare the baseline characteristics of the two treatment groups within study sites and the whole study. In addition, we will use t-tests to compare continuous variables and Chi square tests for categorical variables.

2. Primary objective

The primary objective is to compare the effectiveness of PE and CPT for reducing the severity of PTSD symptoms as measured by CAPS total score. The primary outcome is change of CAPS total score from baseline (pre-treatment) to the average in the six months post-treatment (measured at post-treatment and 3 and 6 months follow-up visits).

Primary analysis: The primary analysis will follow the intent-to-treat (ITT) principle. Participants will be counted in the treatment group to which they were randomized, regardless of the number of sessions they completed. Linear mixed effects models, with time, treatment, treatment by time interaction and site as fixed effects and participant and therapist as random effects, will be used to estimate and compare the primary outcome between PE and CPT. The point estimate and the 95% confidence interval for the mean difference will be provided.

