Secondary analysis: We will provide point estimates and pointwise 95% confidence intervals for the mean differences in the CAPS total scores at the three post-treatment timepoints as well as the mean differences in changes of CAPS total score from baseline at these post-treatment timepoints. We will also compare the longitudinal profiles of CAPS total score (including the mid-treatment and post-treatment scores) between PE and CPT by testing the treatment by time interaction. When data permits, we will explore site variations in treatment effect and also explore the impact of different covariance variance structures (e.g., allowing the variance of therapist random effect to differ by treatment or allowing certain variances or covariances to vary by time). Although we anticipate minimum missing data in CAPS total score, we will perform analyses to examine the missing data patterns and the impact of missing data.

As in CSP #494, we will use the CAPS to derive additional measures of clinical outcomes: response (defined as at least 10-point improvement in severity), loss of diagnosis (response plus no longer meeting DSM symptom criteria), and remission (loss

of diagnosis plus the DSM-5 score that corresponds to a DSM-IV severity score < 20). The observed proportions and their 95% confidence intervals will be provided for each treatment group at each of the follow-up timepoints. Chi-square tests will be used to compare these outcomes between the two treatment groups.

3. Secondary objective

The secondary objective is to compare the effectiveness of PE and CPT for reducing the severity of comorbid mental health problems and service utilization and improving functioning and quality of life.

These secondary outcome measures, listed in Table II.1 below, will be compared between PE and CPT to support the comparative effectiveness of these two treatments in CAPS total score. Except for Brief Addiction Monitor and certain service utilization outcomes (which are categorical measures), all other secondary outcomes are continuous measures and will be analyzed in a manner similar to CAPS total score as described above. Generalized linear mixed effects models (SAS PROC GLIMMIX) will be used to compare the longitudinal profiles of the categorical measures between PE and CPT. Generalized estimating equations may also be used. We do not plan to adjust for multiple comparisons due to the supportive nature of these secondary outcomes.

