Treatment Session 1	0-30 days after randomization
Treatment Session 2-14*	7-21 days after previous session
Mid-Treatment Assessment (Session 6)	0-14 days after session 6
Post Treatment Assessment	0-14 days after final treatment session
3-month Assessment	3 months ±2 weeks after final treatment session
6-month Assessment	6 months ±2 weeks after final treatment session

* The site SC and therapist will make sure Treatment Session 7 is scheduled after the "Mid-Treatment Assessment (session 6)" visit.

K. Rules for handling windows with more than one visit

Visit follows sequentially from previous visit. Thus, it won't be an issue for this study. If a visit is late in the follow-up phase, the late visit will be assigned to the visit with the closest target date.

L. Data inclusion/exclusion decision rules

Plan to use the data from all randomized participants in the analyses, regardless of the number of sessions they have completed. However, for sites with questionable data the study Executive Committee and Data Monitoring Committee will make recommendation to CSR&D Director whether to exclude the data from analyses or not.

M. Definition of compliance

Treatment compliance and termination will be reported and monitored. Regardless of their treatment compliance levels, the data from all participants will be used for analyses.

N. Methods for handling multiple observations

Appropriate methods for analyzing repeated measures data (e.g., mixed effects models, generalized estimating equations) as described in Sections II.H.2 and II.H.3 above.

- O. Use of baseline variables See Section II.H.1 above.
- P. Rules for calculation of derived variables See Section II.H.2 above.
- Q. Use of covariate data See Sections II.H.4 and II.H.5 above.
- R. Rules for stopping the trial, and allowance for them in the analysis See Section II.D.2 above.

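### The primary model compares raw change in CAPS and adjusts for baseline CAPS nowhere; estimating the baseline slope would be a near-free gain in precision (8.6% of the variance under the plan's own components, true size unknown)

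*SAP*

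**What the plan says.** SAP II.H.2 (and Protocol X.D.2 in the same terms) specifies "Linear mixed effects models, with time, treatment, treatment by time interaction and site as fixed effects and participant and therapist as random effects". SAP II.U repeats it: "The mixed effects model will include time, treatment, treatment by time interaction and site as fixed effects, and participant and therapist as random effects". No baseline CAPS term is listed.

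Protocol X.B.1 writes the model out. The response is indexed with "k = 0 indicating baseline and k = 1, 2, 3 indicating the three post-treatment timepoints", so baseline CAPS is an outcome in the model. The fixed effects include both treatment and treatment by time, which gives each arm its own baseline mean. The planning variance in Protocol X.B.2 is the therapist variance, plus the within-subject variance divided by the number of post-treatment scores, plus one further full within-subject variance for baseline. That is the variance of raw change.

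The other places where an adjustment might appear do not supply one:

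- SAP II.O: "Use of baseline variables See Section II.H.1 above". That section holds the baseline comparability tests.
- SAP II.Q: "Use of covariate data See Sections II.H.4 and II.H.5 above". Those sections hold the preference and subgroup analyses.
- Protocol X.B.1 has an optional covariate vector that may hold baseline characteristics. It does not name CAPS, and the SAP does not carry it over.
- The secondary analysis in SAP II.H.2 reports "mean differences in the CAPS total scores at the three post-treatment timepoints as well as the mean differences in changes of CAPS total score", which corresponds to slopes of 0 and 1.

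**The concern.** Baseline CAPS is already collected on everyone and predicts later CAPS. A raw-change contrast subtracts the whole baseline score, including its measurement error. If the regression of post-treatment CAPS on baseline has a slope below 1, this over-corrects: part of any chance baseline difference between the arms stays in the estimate with its sign reversed, and the standard error is larger than it need be.

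What is at stake is precision only. The plan is close to its 90% power target, so a small gain at almost no cost is useful, though the trial does not depend on it.

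**Working it through.** **Inputs.** Protocol X.B.2: variance components from CSP #494 of 36 (therapist), 504 (between-subject) and 174 (within-subject), with 504 + 174 = 678 at baseline and 36 + 678 = 714 at one post-treatment visit. Protocol X.B.3: m = 8 participants per therapist. Protocol X.A: target 5 points; 19.6 "is the standard deviation of the change of CAPS total score from baseline to a specific post-treatment timepoint". SAP I.E: 450 per arm. Two-sided alpha 0.05, normal approximation.

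**1. The plan's own figures.** With t = 3, tau² = 36 + 174/3 + 174 = 268. Then n = 2(1.960 + 1.282)² × 268/25 = 225.3, so 226 per arm and 452 in total, as stated. The inflation factor is 1 + 7 × 36/268 = 1.94, giving 874 to 877 depending on rounding, against 878 stated. For t = 2 I get 923 against 920. The plan reproduces, with raw-change variance.

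**2. Raw change against estimated slope.** The variance per participant, with clustering, is:

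- Raw change: V = 36 + 174/t + 174 + 7 × 36.
- Estimated slope: V = (36 + 504 + 174/t) − 504²/678 + 7 × 36, with slope 504/678 = 0.74.
- SE of the arm difference = √(2V/450).

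| t | V, raw | V, adjusted | Reduction | SE | Power for 5 points |
|---|---|---|---|---|---|
| 3 | 520.0 | 475.3 | 8.6% | 1.520 to 1.453 | 90.8% to 93.1% |
| 2 | 549.0 | 504.3 | 8.1% | 1.562 to 1.497 | 89.3% to 91.6% |

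At t = 3 the gain matches a trial of 900 × 520.0/475.3 = 985 participants. A one-SD chance baseline difference is √(2 × 678/450) = 1.74 points, and raw change leaves 1.74 × (1 − 0.74) = 0.45 points of it in the estimate.

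**3. Would the optional covariate vector do this?** No. It enters as a time-constant main effect and cancels from a change contrast. In a simulated data set, adding baseline CAPS there changed neither the estimate nor its variance.

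**4. How far the gain depends on the components.** They imply a baseline-to-post variance ratio of 678/714 = 0.95. The documents give no separate CAPS ratio or correlation, so what follows is assumption. First hold the SD of change at 19.6 (variance 384) and post variance at 714, with V0 = ratio × 714 and covariance c = (V0 + 714 − 384)/2. Adjusted V is then 850 − c²/V0, and raw V is 520.0 in every row (t = 3).

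| Ratio | Slope | Adjusted V | Reduction | Power |
|---|---|---|---|---|
| 1.0 | 0.73 | 468.4 | 9.9% | 93.4% |
| 0.95 | 0.74 | 475.3 | 8.6% | 93.1% |
| 0.8 | 0.79 | 494.5 | 4.9% | 92.1% |
| 0.7 | 0.83 | 505.6 | 2.8% | 91.6% |
| 0.6 | 0.89 | 514.3 | 1.1% | 91.1% |
| 0.53 | 0.94 | 518.5 | 0.3% | 90.9% |

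The 0.53 is borrowed from the PTSD Checklist SDs in Protocol Table I.2 (11.9²/16.8² = 0.50 in PE, 10.6²/14.2² = 0.56 in CPT), a different, self-report instrument.

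Now keep ratio 0.53 (V0 = 378.4) but let the correlation of baseline with one post-treatment visit vary instead, so c = correlation × √(378.4 × 714). At correlation 0.5, V goes from 708.6 to 671.5, a 5.2% reduction. At 0.36 it goes from 854.2 to 757.5, an 11.3% reduction. The SD of change is then 23.9 and 26.8.

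**5. Participants with no post-treatment score.** Protocol X.B.3 reports that in CSP #494 about 75% had all three scores and the mean number was 2.45. The other 25% therefore averaged (2.45 − 3 × 0.75)/0.25 = 0.8 scores. If those with any score had one each, 25% × (1 − 0.8) = 5% had none; if two each, 25% × (1 − 0.4) = 15% had none. That is 45 to 135 of 900 if it recurred. With such participants spread at random over therapists, the SE at 5% is 1.536 for the planned model and 1.470 for both the covariate and the shared-baseline models. At 15% it is 1.572 against 1.508.

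**The case against.** The strongest reply is that this is a preference. Change from baseline is the declared outcome throughout, the planned model targets it, and the sample size was computed with that model's own variance. Protocol X.B.1 says the simple form was chosen for ease of interpretation. All of that stands, and it is why the point is an optional improvement. It does not remove the gain. Because randomisation gives both arms the same expected baseline, the treatment effect on the post-treatment average and on the change are the same quantity.

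A second reply is that the secondary analysis already covers baseline imbalance. It would make an imbalance visible, but neither a slope of 0 nor a slope of 1 is an estimate of the slope.

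Three stronger readings are tempting, and the documents do not support them:

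- A reader might infer that the primary analysis is biased or underpowered. It is unbiased under randomisation, and it has 90.8% power at t = 3 and 89.3% at t = 2.
- A reader might take 0.3% to 8.6% as a range for the true gain. The 0.3% needs the SD of change to stay at 19.6; with a lower correlation the same variance ratio gives 5.2% or 11.3%. Nor is 8.6% a ceiling, since ratio 1.0 gives 9.9%. It is not an expected value either: the minimum-severity entry criterion may compress baseline variance.
- A reader might infer that repeat CAPS interviews contaminate the baseline. Protocol IV.C.3 repeats the CAPS if more than 30 days pass between Phase 3 and session 1, and the SAP II.J windows allow up to 7 + 30 = 37 days with randomisation by day 7, so a repeat can follow assignment. Nothing shows how often this happens or that it biases anything. It only means that the fix must name the score it uses.

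**Conclusion.** The point holds as a missed efficiency. Baseline CAPS is adjusted for nowhere, and under the plan's own components an estimated slope would lower the variance of the primary contrast by 8.6% at t = 3 and 8.1% at t = 2, or about 2 points of power. These figures rest on compound symmetry, the CSP #494 components and 8 participants per therapist. Away from those components the size is unknown, and the other figures are illustrations, not bounds. Since a slope of 1 is a special case of an estimated slope, the most that can be lost is about one degree of freedom. Worth considering; not a defect that threatens the trial.

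**What to change.** In SAP II.H.2 and II.U and Protocol X.B.1 and X.D.2:

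- Model the three post-treatment CAPS scores with the pre-randomisation CAPS as a covariate with an estimated slope. Keep time, treatment, treatment by time, site, and the participant and therapist random effects. Estimate the average of the three post-treatment differences.
- SAP II.L says "Plan to use the data from all randomized participants in the analyses". To keep participants without a post-treatment score in the fitted data, use instead one shared baseline mean with an unstructured covariance over time. Do not pair the shared mean with compound symmetry: at ratio 0.53 (SD of change 19.6) its variance is 3.5% above raw change (SE 1.547 against 1.520).
- Keep the raw-change model as a sensitivity analysis, with the same pre-randomisation baseline.
- The same model may be used for continuous secondary outcomes with a baseline score (not the satisfaction questionnaire, the PTSD Checklist or the PHQ-9, which have none scheduled). The gain there cannot be sized from the documents.

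**Cost.** No new data, but a small program change and an amendment under Protocol X.G, with review by the coordinating centre director, the Executive Committee and the DMC. Timing matters: SAP II.D.2 has the coordinating centre run treatment comparisons for each DMC report, so the model should be settled before the people choosing it see any comparison by arm. The covariate version drops participants with no post-treatment CAPS (about 5% to 15% if CSP #494 recurs; the plan expects better follow-up), with no loss of precision.
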